8.5 Safety Follow-up Visit/Contact (Visit 14)

The safety follow-up is conducted to capture serious adverse events (SAEs) that occur during the Safety Follow-up Period as well as to follow up on the outcome of adverse events ongoing at the end of the Treatment Period. The safety follow-up may either be conducted as a visit to the site or as a telephone contact. The safety follow-up must be conducted approximately 30 days after the last dose of IMP.

If any new SAEs have occurred since the last assessment at which the patient received IMP, the safety follow-up must, when possible, be a visit to the site.

For adverse events that were ongoing at the end of the Treatment Period and that resolved during the Safety Follow-up Period, the stop date must be recorded. For non-serious adverse events still ongoing at the safety follow-up, the stop date must be recorded as “ongoing”. SAEs must be followed until resolution or the outcome is known.

Patients with a clinical safety laboratory test value that was out-of-range at the Completion or Withdrawal Visit and judged clinically significant must be followed according to accepted medical standards for up to 30 days or until the value normalises or stabilises or a diagnosis or a reasonable explanation has been established. For these patients, safety follow-up visits must be scheduled to allow for a medical examination and/or blood sampling. The investigator must decide whether further safety follow-up visits are required after 30 days. If further safety follow-up visits are made, these must be documented in the patient’s medical record and not in the eCRF.

Patients who withdrew due to elevated AST or ALT values (see section [5.3](#)) should be followed until the values normalise or stabilise or a diagnosis or a reasonable explanation has been established (see section [10.5](#)).

The safety follow-up for patients who withdraw assent/consent must be performed, if at all possible; any information collected will be recorded in the patients’ medical records.

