
The blood and urine drug screen samples will be analysed at the central laboratory.

The additional urine samples will be collected and analysed at the site using dipsticks. If the dipstick evaluation is positive or abnormal, further analysis will be performed at the central laboratory.

The investigator must review (initial and date) the results of the clinical safety laboratory tests as soon as possible after receipt of those results. Out-of-range values must be interpreted by the investigator as “not clinically significant” or “clinically significant” with a comment concerning the planned follow-up. Tests for clinically significant out-of-range values must be repeated, or an appropriate clinical follow-up must be arranged by the investigator and documented on the laboratory report, until the value has stabilised or until the value has returned to a clinically acceptable value (regardless of relationship to IMP). Any value that is out-of-range at the Completion or Withdrawal Visit and judged clinically significant must be followed according to accepted medical standards for up to 30 days or until the value normalises or stabilises or a diagnosis or reasonable explanation has been established. Any out-of-range values followed after the last protocol-specified contact with the patient will be documented in the patient’s medical record.

Clinically significant out-of-range values must be recorded as an adverse event on an *Adverse Event Form*.

The central laboratory will be notified by the sponsor when the biological samples may be destroyed.

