## 12.2 General Methodology for Other Safety Data

Unless otherwise specified, tables, graphs, and listings will be based on the APTS, and the tables will be presented for all patients and by lead-in study and by lead-in treatment.

The denominators for the summaries of a given variable will be based on the number of patients with non-missing values at a given visit or during the assessment period.

Descriptive statistics for the safety variables, both absolute values and change from baselines (baseline at randomisation in lead-in study and OLEXA), will be presented by visit and for the last assessment. All available post-OLEXA assessments will be included in the identification of the last assessment.

The number and percentage of patients with at least one PCS value at any post-baseline assessment time point will be summarized by variable. All available assessments will be included in the evaluation of PCS values.

The number and percentage of patients with values out-of-reference range and/or PCS range will be summarized by variable, visit, and last post-baseline assessment.

For patients with post-baseline PCS values, listings will be provided including all the values for those patients for the variable, with flagging of PCS values and out-of-reference-range values.

The PCS definition will be provided by H. Lundbeck and are stated in [Appendix IV](#).

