#### **12.4 Vital Signs and Weight**

Descriptive statistics for the vital sign parameters will be presented by visit and the last assessment in the Period.

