#### Panel 6 C-SSRS Scores

C-SSRS Score	Related to:
1 Wish to be dead	Suicidal ideation
2 Non-specific active suicidal thoughts	
3 Active suicidal ideation with any methods (not plan) without intent to act	
4 Active suicidal ideation with some intent to act, without specific plan	
5 Active suicidal ideation with specific plan and intent	
6 Preparatory acts or behaviour	Suicidal behaviour
7 Aborted attempt	
8 Interrupted attempt	
9 Non-fatal suicide attempt	
10 Completed suicide (only applicable for the post-baseline assessments)	

In the C-SSRS, non-suicidal self-injurious behaviour is captured as a different behaviour; patients may have reported non-suicidal self-injurious behaviour in addition to suicidal ideation/behaviour. Positive responses to non-suicidal self-injurious behaviour will be summarised separately.

For patients with any post-baseline suicidal behaviour (C-SSRS scores of 6 to 10), listings will be prepared including all C-SSRS scores; C-SSRS scores related to suicidal behavior will be flagged.

All assessments will be regarded as valid for C-SSRS.

Missing C-SSRS scores will not be imputed.

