### **12.6.2 Paediatric Adverse Event Rating Scale (PAERS)**

Note, all assessments will be regarded as valid for PAERS (that is, the criteria that assessment date-date of last IMP must be  $\leq 7$  days will not be applied).

For each item, a severity score will be derived where the analysis value is defined as:

- If *Recently Present*=No, the analysis value will be *Absent*.

Otherwise, the analysis value will be the reported Severity (*Mild*, *Moderate*, *Severe*, or *Extreme*)

The assessments for the PAERS will be prepared according to the description in the [Data Handling Plan](#). For each item 1 to 43, the following parameters will be derived for each analysis phase following a baseline (all assessments within a phase will be included in the evaluation):

- *Worst severity score*:  
Worst severity score of the item (analysis value will be the worst severity)
- *Worsening of severity score compared to baseline*:  
Worsening of the item compared to OLEXA (analysis value will be ‘Yes’ or ‘No’)

If a patient had a worsening of an item, all original assessments at the OLEXA will be listed.

Also graphical presentations of the PAERS will be done.

Item 44 and 45 will only be listed, based on APES.

For further details, see [Data Handling Plan](#).

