## **18.5 Handling Missing or Incomplete Dates/Times**

### **18.5.1 IMP Start and Stop Dates**

In evaluation of valid efficacy and safety assessments (assessment is considered valid if assessment date-date of last IMP  $\leq 7$  days), a missing date of last IMP will be imputed by the latest attended Visit in the study before the safety follow-up.

Exposure with missing IMP start or stop date will not be calculated.

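### SAP 12.2 takes the last assessment from every post-OLEXA value, against the 7-day rule in 18.5.1, so selective off-drug laboratory retests can displace end-of-treatment values

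*SAP*

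**What the plan says.** The SAP describes the end-of-treatment safety value in three ways.

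- SAP 12.2 (general methodology for other safety data) asks for descriptive statistics of absolute values and changes, by visit and at last assessment, and for out-of-range and/or PCS counts by visit and at the last post-baseline assessment. Its rule is: "All available post-OLEXA assessments will be included in the identification of the last assessment".
- SAP 18.5.1, while explaining how to impute a missing last-dose date, states a validity criterion: "In evaluation of valid efficacy and safety assessments (assessment is considered valid if assessment date-date of last IMP" is no more than 7 days.
- SAP 12.4 says vital signs are "presented by visit and the last assessment in the Period". Section 18.1 has Period in its title but defines only baseline.

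Two scales are taken out of the 7-day rule by name. For PAERS, SAP 12.6.2 says every assessment counts ("that is, the criteria that assessment date-date of last IMP must be" within 7 days is not applied). For the C-SSRS, the text under Panel 6 says "All assessments will be regarded as valid for C-SSRS".

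On follow-up, protocol 8.5 says a patient whose final laboratory value was out of range and clinically significant "must be followed according to accepted medical standards for up to 30 days or until the value normalises or stabilises", among other end points. Protocol 9.4.2 adds: "Tests for clinically significant out-of-range values must be repeated, or an appropriate clinical follow-up must be arranged by the investigator". Protocol 10.5 repeats the follow-up instruction. Neither Panel 2 of the protocol nor Table 1 of the SAP schedules laboratory sampling at Visit 14.

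**The concern.** Safety is the primary endpoint, and laboratory values with their changes from OLEXA are part of it. The last-assessment row is where completers and early withdrawals appear together, each at the end of their own treatment. If that row can hold a value taken weeks after the last dose, it no longer describes patients on vortioxetine.

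The replacement would also run one way. A patient with an unremarkable final sample has no scheduled reason to be sampled again and keeps the on-drug value. A patient with a clinically significant final abnormality may be sampled again off drug, and that later value would become the last one. Two programmers following 12.2 and 18.5.1 respectively could produce different tables from the same data.

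**Working it through.** No figure in the plan depends on this rule, so there is none to reproduce. The check sets the passages against each other and then asks how large the effect could be.

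**1. Would a follow-up retest count as the last assessment?** Protocol 8.5 places safety follow-up about 30 days after the last dose.
- Under 12.2 read literally: yes, because the retest is a post-OLEXA value.
- Under 18.5.1: no, because 30 days exceeds 7.
- Under 12.4 (vital signs): undetermined, because Period has no definition.

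**2. Is such a value off drug?** Protocol 1.1.3.1 gives a mean adult elimination half-life of 66 h. Fraction remaining after t days = 0.5^(24t/66):
- day 2: 60.4%
- day 7: 17.1%
- day 14: 2.9%
- day 30: 0.05%

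This describes washout of drug, not recovery of a laboratory value. It shows only that a day-30 sample is not an on-treatment sample.

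**3. Could the value reach the database?** Protocol 8.5 and Panel 2 footnote b keep visits beyond 30 days out of the eCRF. Protocol 9.4.2 sends values followed after the last protocol-specified contact to the medical record. Protocol 11.1.3 has the central laboratory transfer its results. That an earlier retest is captured is therefore a reasonable inference, but it is not stated.

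**4. Which outputs are exposed?**
- Exposed: laboratory descriptive statistics and change at last assessment, and laboratory out-of-range/PCS counts at last assessment.
- Not exposed: the any-time PCS count ("The number and percentage of patients with at least one PCS value at any post-baseline assessment time point will be summarized by variable"); the by-visit rows (SAP 18.4 windows unscheduled scale assessments and says nothing of laboratory retests); the DILI summaries, which use the maximum or most severe value (12.3.3); and the ECG shift tables, which end at Withdrawal/Completion (12.5).
- Values out of reference range but not PCS have no any-time count in 12.2. For them the only summaries are by visit and at last assessment.

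**5. Illustration of size; every share is an assumption.** N = 850 is used for scale only (1200 × 0.85 × 0.85 = 867 and 1200 × 0.80 × 0.85 = 816 bracket it). Let p be the share with a clinically significant out-of-range final value on a given test, q the share of those retested off drug and in the database, and r the share of retests back in range. The flagged part of the last-assessment count is N·p under the 7-day rule with a day-30 retest, and N·p·(1 − q·r) without it.
- p = 3%: 850 × 0.03 = 25.5. With q = 0.25 and r = 0.5 it becomes 25.5 × 0.875 = 22.3. With q = 0.5 and r = 0.9 it becomes 25.5 × 0.55 = 14.0. With q = 1 and r = 0.9 it becomes 25.5 × 0.10 = 2.55.
- p = 1%: 8.5 falls to between 7.4 and 0.85 over the same range of q and r.
- p = 5%: 42.5 falls to between 37.2 and 4.25.

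The relative fall in the flagged part is q·r, which is 12.5% to 90% here. The reported row also contains out-of-range values not judged clinically significant, which prompt no follow-up. If their share is u, the relative fall in the whole row is p·q·r/(p + u). With u = p, for example, the range halves to 6.25% to 45%. The documents give none of p, q, r or u.

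**The case against.** The strongest reply is that 18.5.1 already settles the matter. Exempting PAERS and the C-SSRS by name makes sense only if the 7-day criterion is the default for other safety data, and under that default a day-30 retest is excluded. The Data Handling Plan, which is not among the documents, may say so. This is a fair reading and may be what was intended. But 12.2 says all available rather than all valid and refers to neither 18.5.1 nor the Data Handling Plan on this point, and 18.5.1 gives its criterion in passing under a heading about dosing dates. The conflict in the text stands.

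The reply also rules out several stronger readings that a reader might infer.

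- That the protocol requires an off-drug repeat sample after every abnormal final value. It does not. Section 9.4.2 allows another clinical follow-up instead, sections 8.5 and 10.5 speak of examination and/or blood sampling, and all three concern values judged clinically significant.
- That abnormality counts in general are understated. Only the laboratory last-assessment displays are exposed. Clinically significant values must also be recorded as adverse events (9.4.2), and 12.2 lists all values of a variable for patients with a post-baseline PCS value.
- That patients withdrawn for raised ALT or AST are the worst hidden. Their peaks remain in the maximum-based DILI tables, listings and plots.

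Finally, no decision rule uses the last-assessment row. The primary objective is met by an overall clinical evaluation (protocol 17.10.1). That limits the consequence but does not remove the inconsistency.

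**Conclusion.** The point holds as an unreconciled rule with a selective effect. SAP 12.2, 12.4 and 18.5.1 do not agree on what the last assessment is, and 12.2 taken literally admits off-drug laboratory retests that are prompted only by clinically significant final values. The laboratory last-assessment counts can then be too low, and the change to last assessment can be shifted towards recovery.

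This rests on two assumptions: that 12.2 is programmed as written, and that retests within about 30 days are in the database. The size is not estimable from the documents. A reader might infer a definite understatement, such as half or more of the abnormal values, but that would need nearly every flagged patient to be retested and would ignore out-of-range values that prompt no follow-up. The ranges above show direction and sensitivity, not an estimate. The change is worth making because the row belongs to a primary-endpoint display and the correction costs almost nothing.

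**What to change.** In SAP 12.2 and 12.4, define the last assessment as the last post-OLEXA value, up to and including the Completion/Withdrawal Visit, that is valid under 18.5.1 (no more than 7 days after last IMP). Exclude later follow-up retests, and define Period in 18.1 to match. Both conditions are needed: the 7-day limit alone still admits a retest taken within 7 days of the last dose, and the visit limit alone admits a Withdrawal Visit held long after it.

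Keep all available assessments for the any-time PCS count and the DILI outputs. List post-treatment retests separately as recovery data.

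The cost is SAP wording and one derivation flag, with no change to study conduct. There is one small downside. Post-baseline laboratory samples are scheduled only at Week 4 and at Completion/Withdrawal, so a withdrawn patient whose only post-baseline sample came more than 7 days after last IMP would have no value in the last-assessment row. Report how many such patients there are and list their values.

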21. The patient has clinically significant abnormal vital signs at the Completion Visit (Visit 12) of Study 12709A or 12710A and considered a potential safety risk by the investigator.

22. The patient has one or more clinical laboratory test values outside the reference range, based on the latest blood and urine sample results in the lead-in study, that are of potential risk to the patient's safety, or the patient has, according to the latest blood sample:

- a serum creatinine value >1.5 times the upper limit of the reference range
- a serum total bilirubin value >1.5 times the upper limit of the reference range
- a serum alanine aminotransferase (ALT) or aspartate aminotransferase (AST) value >2 times the upper limit of the reference range

23. The patient has an abnormal thyroid stimulating hormone (TSH) level based on the latest blood sample results in the lead-in study. Patients with thyroid disease may be enrolled in the study provided they are stable and euthyroid.

24. The patient has, at the Completion Visit (Visit 12) of Study 12709A or 12710A:

- an abnormal ECG that is, in the investigator's opinion, clinically significant
- a QTcF interval >450 ms (based on the Fridericia correction where $QT_{cF} = QT/RR^{0.33}$)

25. The patient has a disease or takes medication that could, in the investigator's opinion, interfere with the assessments of safety, tolerability, or efficacy, or interfere with the conduct or interpretation of the study.

26. The patient is, in the investigator's opinion, unlikely to comply with the protocol or is unsuitable for any reason.

27. The patient has in the investigator's clinical judgement a significant risk of suicide OR

- answers "yes" to the C-SSRS suicidal ideation questions 4 or 5 OR
- answers "yes" to suicidal behaviour on the C-SSRS within the last 12 months)

28. The patient receives on-going current psychotherapy that is planned to be intensified. Interpersonal psychotherapy (IPT) or cognitive behavioural therapies (CBT) are not allowed.

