16.1 Primary Endpoint

Safety:

- adverse events (AEs)
- tolerability including assessment based on PAERS
- Tanner score
- absolute values and changes from Baseline Extension A in clinical safety laboratory tests, vital signs, weight, height, and ECG parameters
- length of menstrual cycle
- potentially clinically significant clinical safety laboratory test values, vital signs, weight, and ECG parameter values relative to Baseline Extension A
- C-SSRS categorisation based on C-CASA definitions (1, 2, 3, 4, and 7)

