## 3 Endpoints

### 3.1 Primary Endpoint

Safety and tolerability:

- adverse events (AEs)
- PAERS assessment
- Tanner score
- absolute values and changes from OLEXA in clinical safety laboratory tests, vital signs, height, weight and ECG parameters
- length of menstrual cycle

- potentially clinically significant clinical safety laboratory test values, vital signs, weight, and ECG parameter values relative to OLEXA
- C-SSRS categorisation

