## **Appendix IV**

### **PCS Criteria**

## PCS Criteria

**Table 2 Lundbeck PCS Criteria for Clinical Safety Laboratory Tests**

Laboratory Test	CDISC Term	Unit	PCS LOW	PCS HIGH
Haematology / Coagulation				
B-haemoglobin	HGB	g/dL	≤ 9.5 (women); ≤ 11.5 (men)	≥ 16.5 (women); ≥ 18.5 (men)
B-erythrocytes (red cell count)	RBC	x 10E12/L	≤ 3.5 (women); ≤ 3.8 (men)	≥ 6.0 (women); ≥ 7.0 (men)
B-haematocrit (packed cell volume)	HCT	V/V	≤ 0.32 (women); ≤ 0.37 (men)	≥ 0.50 (women); ≥ 0.55 (men)
B-MCV (mean cell volume)	MCV	fL	≤ 0.8 x LLN	≥ 1.2 x ULN
B-total leucocyte (white cell count)	WBC	x 10E9/L	≤ 2.8	≥ 16
B-neutrophils/leucocytes	NEUTLE	%	≤ 20	≥ 85
B-eosinophils/leucocytes	EOSLE	%		≥ 10
B-basophils/leucocytes	BASOLE	%		≥ 10
B-lymphocytes/leucocytes	LYMLE	%	≤ 10	≥ 75
B-monocytes/leucocytes	MONOLE	%		≥ 15
B-thrombocytes (platelet count)	PLAT	x 10E9/L	≤ 75	≥ 600
P-INR (prothrombin ratio)	INR	Ratio		≥ 2.0
B-prothrombin time	PT	Sec		≥ 18
Liver				
S-aspartate aminotransferase	AST	IU/L		≥ 3 × ULN
S-alanine aminotransferase	ALT	IU/L		≥ 3 × ULN
S-bilirubin	BILI	µmol/L		≥ 34
S-bilirubin, direct	BILDIR	µmol/L		≥ 12
S-bilirubin, indirect	BILIND	µmol/L		≥ 22
S-alkaline phosphatase	ALP	IU/L		≥ 3 × ULN
S-gamma glutamyl transferase	GGT	IU/L		≥ 200
S-alpha-glutathione S-transferase (alpha-GST)	GSTAL	µg/L		≥ 20
Kidney				
S-creatinine	CREAT	µmol/L		≥ 1.5 x ULN
B-urea nitrogen (BUN)	BUN	mmol/L		≥ 11
S-uric acid (urate)	URATE	µmol/L		≥ 510 (women); ≥ 630 (men)
Electrolytes				
S-sodium (natrum)	SODIUM	mmol/L	≤ 125	≥ 155
S-potassium (kalium)	K	mmol/L	≤ 3.0	≥ 6.0
S-calcium	CA	mmol/L	≤ 1.8	≥ 3.0
S-chloride	CL MG	mmol/L	≤ 90	≥ 117
S-magnesium	PHOS	mmol/L	≤ 0.6	≥ 1.3
S-phosphate (phosphorus, (inorganic)	BICARB	mmol/L	≤ 0.65	≥ 1.95
S-bicarbonate		mmol/L	≤ 12	≥ 38

Endocrine / Metabolic				
B-glucose, non-fasting/unknown	GLUC	mmol/L	≤ 3.4	≥ 9.4
B-glucose, fasting	GLUC	mmol/L	≤ 3.0	≥ 6.0
S-glucose, non-fasting/unknown	GLUC	mmol/L	≤ 3.9	≥ 11.1
S-glucose, fasting	GLUC	mmol/L	≤ 3.5	≥ 7.0
B-glycosylated haemoglobin, fasting	HBA1C	%		≥ 6.5
S-prolactin	PROLCTN	mIU/L		≥ 1350
S-thyrotropin/TSH	TSH	mIU/L	≤ 0.3	≥ 5.5
S-protein (total)	PROT	g/L	≤ 45	≥ 95
S-albumin	ALB	g/L	≤ 27	
Lipids				
S-cholesterol total, non-fasting/unknown	CHOL	mmol/L		≥ 7.8
S-cholesterol total, fasting	CHOL	mmol/L		≥ 6.2
S-triglycerides, non-fasting/unknown	TRIG	mmol/L		≥ 5.65
S-triglycerides, fasting	TRIG	mmol/L		≥ 4.2
S-LDL cholesterol, non-fasting/unknown	LDL	mmol/L		≥ 5.3

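### The planned PCS counts for laboratory values and ECG intervals mix abnormalities already present at OLEXA with new ones; add a count by OLEXA status beside them

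*SAP*

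**What the plan says.** SAP 3.1 lists as part of the primary endpoint "potentially clinically significant clinical safety laboratory test values, vital signs, weight, and ECG parameter values relative to OLEXA". Protocol 16.1 has the same item, with Baseline Extension A in place of OLEXA.

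SAP 12.2 gives the counting rules:
- The any-time count: "The number and percentage of patients with at least one PCS value at any post-baseline assessment time point will be summarized by variable".
- What enters it: "All available assessments will be included in the evaluation of PCS values".
- A second summary: "The number and percentage of patients with values out-of-reference range and/or PCS range will be summarized by variable, visit, and last post-baseline assessment".
- The denominator: "The denominators for the summaries of a given variable will be based on the number of patients with non-missing values at a given visit". Summaries not tied to one visit use the patients with a value at any time in the period. Patients already PCS at OLEXA are not removed.

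The limits are in SAP Appendix IV. Table 2 (laboratory) uses fixed values or multiples of the reference limits throughout. Table 3 (ECG) has fixed limits for PR, QRS, QT and RR. For QTcB and QTcF the high criterion is a value above 500 or an increase above 60, so the absolute part suffices alone. Heart rate needs both a level and a change. In Table 4, weight, BMI and most vital-sign criteria include a change from baseline.

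**The concern.** An endpoint described as relative to OLEXA leads a reader to expect that the patient's state at OLEXA has been taken into account. It can enter in two ways: through the counting rule or through the PCS criterion itself. For laboratory values and ECG intervals it enters through neither.

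The study has no concurrent control arm, so within-patient comparison carries much of the interpretation. A percentage that mixes persisting and new abnormalities does not show how many patients became PCS during the extension. The tables are also split by lead-in treatment, so differences already present at OLEXA would carry over into the post-baseline percentages.

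**Working it through.** **1. Endpoint against counting rule.** SAP 3.1 asks for PCS relative to OLEXA. SAP 12.2 requires one PCS value after baseline and nothing about OLEXA. The rule yields new cases only if the criterion contains a change term. Table 2 has none in any row. In Table 3, PR, QRS, QT and RR have none.

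**2. A check within Table 3.** RR and heart rate are the same quantity: 60,000 / 1200 = 50 beats/min and 60,000 / 500 = 120 beats/min. Low heart rate is PCS only below 50 with a decrease of at least 15, but RR above 1200 ms is PCS with no change required. A patient with a stable slow rate at OLEXA and at Week 4 is a post-baseline PCS case for RR and not for heart rate, on the same ECG. RR below 500 against heart rate of 120 or more shows the same mismatch.

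**3. What entry criteria remove (Protocol 5.2).**
- ALT/AST above 2×ULN is excluded; PCS starts at 3×ULN.
- Creatinine above 1.5×ULN is excluded; PCS starts at 1.5×ULN.
- QTcF above 450 ms is excluded; the absolute PCS limit is above 500.
- Bilirubin above 1.5×ULN is excluded; the PCS limit is 34 µmol/L, and the ULN needed to compare them is not given.
- Abnormal TSH is excluded under criterion 23. Clinically significant abnormal ECGs (24) and clinically relevant arrhythmia or bradycardia diagnosed in the lead-in (19) are also excluded.
- For other laboratory tests, criterion 22 begins "The patient has one or more clinical laboratory test values outside the reference range, based on the latest blood and urine sample results" but excludes only if the value is a potential risk to the patient's safety.

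Protocol 9.1.1 bases laboratory eligibility on the latest available lead-in result, which need not be the Visit 12 sample that serves as OLEXA. The question therefore mainly concerns haematology, GGT, ALP, CRP, prolactin and PR/QRS/QT/RR. Prolactin belongs to the hormone panel, first drawn for this study at Visit 1 (Protocol 9.4.2).

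**4. Size, as an illustration only.** The sole relevant figure in the plan is the planned number of patients, about 850. It reproduces: 1200 × (1 − dropout) × 0.85 gives 867 at 15%, 841.5 at 17.5% and 816 at 20%.

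Three rates are assumed, because the documents give none:
- b, the share PCS at OLEXA: 0-5%
- p, the share of those PCS again afterwards: 50-80%
- i, new PCS among the rest: 1-2%

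Planned count = 850 × [b·p + (1 − b)·i]. New cases = 850 × (1 − b)·i, out of 850 × (1 − b).

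| b | p | i | Pre-existing | New | Planned count | Pre-existing share |
|---|---|---|---|---|---|---|
| 0% | any | 1% | 0 | 8.5 | 8.5 (1.0%) | 0% |
| 1% | 50% | 2% | 4.25 | 16.83 | 21.08 (2.5%) | 20% |
| 2% | 80% | 1% | 13.6 | 8.33 | 21.93 (2.6%) | 62% |
| 5% | 80% | 1% | 34.0 | 8.08 | 42.08 (5.0%) | 81% |

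In the third row the new-onset figure would be 8.33 of 833, or 1.0%, against a reported 2.6%. For b of 1% or more within these ranges, the share runs from 20% to 81%.

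**The case against.** Five counter-arguments deserve weight.

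- **OLEXA is not drug-free.** It is Visit 12 of placebo-controlled, active-reference studies, 12 weeks after the lead-in baseline. For patients given vortioxetine in the lead-in, a PCS value at OLEXA may have arisen on the drug. A reader might infer that the all-patient count should be replaced by a new-onset count, or that pre-existing means unrelated to vortioxetine. The documents support neither, and demoting the full count could hide persistent on-drug abnormalities. This objection stands and shapes the fix.
- **OLEXA is not the only reference.** SAP 12.2 also presents change from the lead-in randomisation baseline. This stands.
- **Other outputs separate new from old.** SAP 12.3.4 plans lipid and glucose shift tables, and SAP 12.5 a normal-to-abnormal ECG shift table. Findings judged clinically significant must be recorded as adverse events (Protocol 9.4.1), which SAP 12.1.2.3 classifies as lead-in or treatment-emergent. The listings in SAP 12.2 show all values with PCS flags. So it would be wrong to infer that no planned output separates them or that information is lost. These outputs still give no new-versus-existing PCS count for each laboratory variable or ECG interval.
- **The endpoint phrase may only mean that change-based criteria use OLEXA.** That reading is possible, but it leaves the phrase without content for laboratory values, which the endpoint names first. Clarification is needed either way.
- **The summaries are descriptive.** No test depends on them, and Protocol 17.10.1 addresses the primary objective by an overall clinical evaluation. This limits the consequence but does not make the table more informative.

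**Conclusion.** The point holds as an inexpensive improvement. From the text alone, SAP 12.2 mixes pre-existing and new PCS cases for laboratory variables, for PR, QRS, QT and RR, and for the absolute part of the QTc criteria. Pre-existing PCS should be rare for ALT/AST, creatinine and QTcF above 500.

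A reader might take the 20% to 81% range as an estimate of how distorted the tables will be. The documents do not support that: the range rests wholly on assumed rates, and the effect is zero if nobody is PCS at OLEXA. The Data Handling Plan is not among the documents and might contain a rule, but SAP 12.2 does not refer to it for PCS values.

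**What to change.** Keep the planned all-patient PCS count. Beside it, for each laboratory and ECG-interval variable, add:

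1. The number and percentage with a post-OLEXA PCS value among patients not PCS at OLEXA, with those patients who have at least one post-OLEXA value as the denominator.
2. A separate row for patients already PCS at OLEXA, and another for patients with a missing OLEXA value.

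A PCS shift table from OLEXA would serve equally well. Present the additions by lead-in treatment, and repeat them against the lead-in randomisation baseline where the variable was collected there. State in SAP 12.2 and Appendix IV that post-baseline, and the increase and decrease terms, refer to OLEXA.

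The data are already collected. The cost is a short SAP addition, a baseline filter in the table program, a few extra rows, and slightly smaller denominators for the new-onset row.
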